All patients will have a screening/baseline visit (Visit 1), at which they will be asked if they own a smart device and use different applications on their smartphones. A baseline ACT score for all patients and BMQ, BIPQ, Mini-AQLQ, and WPAI questionnaire responses, for patients 18 years of age or older, will be collected. At Visit 1, patients in the DS group will be trained on the use of the eMDPI (including instructions on how to use both the eMDPIs and the App). Upon demonstrating competency, patients in the DS group will have their maintenance ICS with LABA switched to the FS eMDPI (at a dose of fluticasone comparable to their most recent current ICS dose) and their rescue treatment switched to the Albuterol eMDPI. All other asthma maintenance medications, except for ICS with LABA, may be continued. The iHCP can add another controller medication other than an ICS with LABA, including a biologic, to the DS patient's treatment, if needed. Patients in the SoC group will be reimbursed or given a voucher to use to purchase their existing maintenance ICS with LABA and rescue medications. Patients in the DS group will receive a new FS eMDPI device at Visit 1 and 1 FS eMDPI device and 1 Albuterol eMDPI device at Visit 2. Periodically after Visits 1 and 2, patients will be shipped a new FS eMDPI device, which they will need to pair with the App. The patient will immediately stop using the old device and switch to the new device. Extra Albuterol eMDPI devices may be shipped as needed, based on the clinical judgment of the investigator. Upon receipt, the patient will pair the new device with the App and will immediately stop using the old device and switch to the new device. To trigger direct-to-patient (DTP) shipments, after Visit 1, the investigational center will receive periodic email reminders to access the interactive response technology (IRT) system to confirm the dose of test IMP to be shipped to the patient. Confirmation of the dose is required before the next shipment can be sent.

Investigational centers will receive similar instruction regarding features of the App, as well as features of the associated common dashboard, which mirrors the digital information obtained

from the eMDPIs and the App, including frequency and times of SABA rescue use and associated inspiratory flow parameters measured by the eMDPI with each inhalation.

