The SoC group will be followed according to the clinical judgment of the investigator; the asthma of patients in the SoC group will be managed in a manner consistent with the clinical judgement of the investigator and based on asthma management guidelines (eg, GINA). Similar to the management of the SoC group, the DS group patients will be followed by the investigational centers with the addition of objective information on FS eMDPI and Albuterol eMDPI usage being available to both patients and investigational centers through the App and the dashboard, respectively. The iHCPs will check the dashboard at least once a week and use this information, along with any other additional information about the patient, as per their clinical judgement, to modify patients' asthma management. The investigator may, if indicated, modify the patient's regime, including adding asthma controllers or biologics as otherwise clinically indicated in the judgement of the investigator. Clinically Driven Assessments for both groups, if necessary, should be arranged, per the clinical judgement of the iHCP managing the patient, and can be via a telephone call or an on-site visit.

For all patients, at Visit 2, Visit 3, and any Clinically Driven Assessments, if necessary, the iHCP will record answers to Asthma Management questions, including discussions regarding adherence, or inhaler technique, treatment adjustments, or additions of new treatments, including biologic medication usage. Additionally, in the case of a Clinically Driven Assessment (for patients in the DS group), the iHCP will be asked whether or not the contact with the patient was originated from the iHCP interaction with the dashboard.

Visit 2 (if it is an in-person visit) will include dispensing of new inhalers to the DS group patients and return of used or unused inhalers that were dispensed to the patients previously. New FS eMDPI devices will continue to be shipped directly to patients periodically after Visit 2 until the end of treatment. The ACT will be completed and scores registered.

At the end of the treatment period (24 weeks), final assessments of the DS and SoC groups will be completed, as specified in Table 5, and the rest of the inhalers that were dispensed to the DS group patients will be returned. A follow-up telephone call will be made by the investigational

center to all patients, 2 weeks later, and will confirm that the DS group patients have returned to their previous asthma treatments.

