It should also be noted that no specific clinical decisions are being mandated. One secondary objective of this study is to describe how clinicians actually use the information provided by the DS to manage their patients.

Figure 2: Overall Study Schematic Diagram

Visit 1 (SCREENING/BASELINE)

Inclusion/exclusion criteria, informed consent, medical history, medications, vital signs, AEs, ADEs, baseline ACT, Mini-AQLQ, WPAI, BMQ, BIPQ, randomization

DS GROUP (24 weeks)

DS: FS eMDPI and Albuterol eMDPI, App, provider-facing dashboard (investigational centers)

SoC GROUP (24 weeks)

Standard of care

Visit 2 (12 weeks after Visit 1)

Concomitant medications, AEs, ADEs, ACT, Asthma Management questions, eMDPI collection and accountability, eMDPI dispensing, if necessary

Visit 3 (End of Treatment, 12 weeks after Visit 2)

Medications, AEs, ADEs, post-intervention ACT, Mini-AQLQ, WPAI, BMQ, BIPQ, SUS (DS group and iHCPs), Asthma Management questions, eMDPI collection and accountability

FOLLOW-UP (2 weeks after Visit 3)

Telephone call: AEs, ADEs, medications, and confirm patients in the DS group have returned to previous asthma treatment

Clinically Driven Assessments (if necessary)

AEs, ADEs, concomitant medications, and Asthma Management questions

DTP Shipments for DS Group

FS eMDPI: Weeks 3, 6, 9, 12 (if Visit 2 is not an in-person visit), 15, 18, and 21.

Albuterol eMDPI: May be shipped if Visit 2 is not an in-person visit. Extra devices may be shipped as necessary.

ACT=Asthma Control Test; ADE=adverse device effects; AEs=adverse events; Albuterol eMDPI= albuterol sulfate electronic multidose dry powder inhaler; App=smart device application; BIPQ=Brief Illness Perception Questionnaire; BMQ=Beliefs about Medicines Questionnaire; DTP= direct-to-patient; DS=Digital System; FS eMDPI=fluticasone propionate/salmeterol electronic multidose dry powder inhaler; iHCP=investigational center health care providers; Mini-AQLQ=Mini Asthma Quality of Life Questionnaire; SoC=Standard of Care; SUS=System Usability Scale; WPAI= Work Productivity and Activity Impairment. Note: The BIPQ, BMQ, Mini-AQLQ, WPAI, and SUS questionnaires will be completed by patients 18 years of age or older.

CLN0035849 Version 2.0 Approved Page 39 of 98

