3.5. Schedule of Study Procedures and Assessments

Study procedures and assessments with their time points are presented in Table 5. Detailed descriptions of each method of procedures and assessments are provided in Section 6 (efficacy assessments) and Section 7 (safety assessments). Study procedures and assessments by visit are listed in Appendix B.

Table 5: Study Procedures and Assessments

Study period	Screening/ Baseline visit	Treatment period (24 weeks)					Follow- up telephone call ^a	Clinically driven assessment(s) (if necessary)			
									End of treatment/ ET visit		
Visit number	Visit 1	DTP	DTP	DTP	Visit 2 ^b		DTP	DTP	Visit 3		
Treatment week		W3	W6	W9	W12	W15	W18	W21	W24	W26	
Day and allowed time windows	Day 1 ^c				84 days ±3 days				168 days +3 days	182 +7 days	
Procedures and assessments											
Informed consent/assent	X										
Inclusion and exclusion criteria	X										
Medical history	X										
Current medication and treatment history related to asthma	X										
Inform patients of study restrictions and compliance requirements	X										
ACT ^d	X				Xe				X		
Mini-AQLQ and WPAI ^d	X								X		
BMQ-S11 and BIPQ ^d	X								X		
Assign patient number and provide unique email account for DS group patients	X										
Train DS group in use of test IMP	X										
Dispense test IMP to DS group											
FS eMDPI ^f	X	X	X	X	X	X	X	X			X
Albuterol eMDPI ^g	X				X						
Dose confirmation of test IMP in IRT ^h	X	X	X	X	X	X	X	X			X ⁱ
Registration and onboarding (App)	X										

Version 2.0

CLN0035849

Page 41 of 98

Approved

Study period	Screening/ Baseline visit	Treatment period (24 weeks)						Follow- up telephone call ^a	Clinically driven assessment(s) (if necessary)		
									End of treatment/ ET visit		
Visit number	Visit 1	DTP	DTP	DTP	Visit 2 ^b	DTP	DTP	DTP	Visit 3		
Treatment week		W3	W6	W9	W12	W15	W18	W21	W24	W26	
Day and allowed time windows	Day 1 ^c				84 days ±3 days				168 days +3 days	182 +7 days	
Procedures and assessments											
Adverse events and adverse device effects inquiry	X				X				X	X	X
iHCP will ask Asthma Management questions regarding adherence, inhaler technique, treatment adjustments, and biologic medication usage					X				X		X
Vital signs measurement	X								X		
Concomitant medication inquiry	X				X				X		X
Administer post- intervention PRO (SUS) to DS group patients ^j									X		
Administer SUS to iHCPs									X		
Test IMP collection and accountability					X				X		

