Remove App from the patient's smart device (DS group)									X		
Confirmation that patient has returned to previous asthma treatment (DS group)		2.11			II Con the a l					X	

^a End of study is defined as the follow-up telephone call for the last patient.

CLN0035849 Version 2.0 Approved Page 42 of 98

b This visit may be in-person or remote.
c Screening and enrollment are expected to occur on the same day. The maximum allowable duration between screening and enrollment is 7 days.

Clinical Study Protocol with Amendment 01

- d The ACT is to be completed first by all patients, followed by the Mini-AQLQ, WPAI questionnaire, BMQ, and then the BIPQ, all to be completed by patients 18 years of age or older, and should precede any discussion between the patient and investigational center personnel.
- ^e If necessary, this questionnaire may be administered by telephone for this visit.
- f At Visit 1, patients will be provided the test IMP, along with training on use and proper technique, by the investigational centers. New FS eMDPI devices will be shipped directly to the patient periodically after Visits 1 and 2. Upon receipt, the patient will pair the new device with the App. The patient will immediately stop using the old device and switch to the new device. If Visit 2 is in-person at the investigational center, a new FS eMDPI device will be dispensed at that visit.
- ^g Patients will receive an Albuterol eMDPI device, along with training on use and proper technique, at Visit 1 [Day 1] and Visit 2 [Week 12]). Extra Albuterol eMDPI devices may be shipped as needed, based on the clinical judgment of the investigator. Upon receipt, the patient will pair the new device with the App. The patient will immediately stop using the old device and switch to the new device.

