- h To trigger DTP shipments, after Visit 1, the investigational center will receive periodic email reminders to access the IRT system to confirm the dose of test IMP to be shipped to the patient. Confirmation must occur within ±2 days of the email date and is required before the next shipment can be sent. The investigational center will be asked to confirm the dose of FS eMDPI and to specify whether an Albuterol eMDPI should be included in the next shipment (if not already scheduled). The 3-day visit windows do not apply to dose confirmation. Email reminders will be triggered based on the date of the previous visit or DTP shipment. If there is a need to send an additional DTP shipment outside of the regularly scheduled shipments (eg, for an additional or replacement device), it will be done in addition to the scheduled shipments.
- ⁱ Dose confirmation at a Clinically Driven Assessment visit should be performed only if the patient's dose is being changed at this visit.
- ^j The SUS should be the last questionnaire provided to patients, 18 years of age or older, at the end of treatment visit or at the ET visit. Each investigational center will receive 1 SUS questionnaire, regarding the use of the dashboard, to complete following the last patient visit at the investigational center.

ACT=Asthma Control Test; App=smart device application; BIPQ=Brief Illness Perception Questionnaire; BMQ-S11=Beliefs about Medicines Questionnaire-Specific; DS=Digital System; DTP=direct-to-patient; eMDPI=multidose dry powder inhaler with integrated electronic module; ET=early termination; FS=fluticasone propionate/salmeterol; iHCP=investigational center health care provider; IMP=investigational medicinal product; IRT=interactive response technology; Mini-AQLQ=Mini Asthma Quality of Life Questionnaire; PRO=patient-reported outcome; SUS=System Usability Scale; W=week; WPAI=Work Productivity and Activity Impairment.

CLN0035849 Version 2.0 Approved Page 43 of 98

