5. TREATMENTS

5.1. Investigational Medicinal Products Used in the Study

The DSs consist of 4 devices each:

Test IMPs:

- FS eMDPI DS with 4 component devices:
 - Device 1: FS eMDPI
 - Device 2: Patient-facing smart device App (same for both IMPs)
 - Device 3: DHP (Cloud solution, same for both IMPs)
 - Device 4: Provider-facing dashboard (same for both IMPs)
- Albuterol eMDPI DS with 4 component devices:
 - Device 1: Albuterol eMDPI
 - Device 2: Patient-facing smart device App (same for both IMPs)
 - Device 3: DHP (Cloud solution, same for both IMPs)
 - Device 4: Provider-facing dashboard (same for both IMPs)

At Visit 1, patients in the DS group will be trained on the use of the eMDPI (including instructions on how to use both the eMDPIs and the App). Upon demonstrating competency, patients in the DS group will have their maintenance ICS with LABA switched to the FS eMDPI (at a dose of fluticasone comparable to their most recent current ICS dose) and their rescue treatment switched to the Albuterol eMDPI. All other asthma maintenance medications, except for ICS with LABA, may be continued. The iHCP can add another controller medication other than an ICS with LABA, including a biologic, to the DS patient's treatment, if needed. Patients in the SoC group will be reimbursed or given a voucher to use to purchase their existing maintenance ICS with LABA and rescue medications. Patients in the DS group will receive a new FS eMDPI device and 1 Albuterol eMDPI device at Visit 1 and 1 FS eMDPI device at Visit 2. Periodically after Visits 1 and 2, patients will be shipped a new FS eMDPI device, which they will need to pair with the App. The patient will immediately stop using the old device and switch to the new device. Extra Albuterol eMDPI devices may be shipped as needed, based on the clinical judgment of the investigator. Upon receipt, the patient will pair the new device with the App and will immediately stop using the old device and switch to the new device. To trigger DTP shipments, after Visit 1, the investigational center will receive periodic email reminders to access the IRT system to confirm the dose of test IMP to be shipped to the patient. Confirmation of the dose is required before the next shipment can be sent.

Patients will be instructed to return all inhalers to the investigational center at Visit 2 and at the end of treatment visit or Early Termination (ET) visit.

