All patients will have a screening/baseline visit (Visit 1), at which they will be asked if they own a smart device and use different applications on their smartphones. A baseline ACT score for all patients, and BMQ, BIPQ, Mini-AQLQ, and WPAI questionnaire responses for patients 18 years of age or older will be collected. At Visit 1, patients in the DS group will be trained on the use of the eMDPI (including instructions on how to use both the eMDPIs and the App). Upon demonstrating competency, patients in the DS group will have their maintenance inhaled corticosteroid (ICS) with long-acting beta₂ agonist (LABA) switched to the FS eMDPI (at a dose of fluticasone comparable to their most recent current ICS dose) and their rescue treatment switched to the Albuterol eMDPI. All other asthma maintenance medications, except for ICS with LABA, may be continued. The iHCP can add another controller medication other than an

ICS with LABA, including a biologic, to the DS patient's treatment, if needed. Patients in the SoC group will be reimbursed or given a voucher to use to purchase their existing maintenance ICS with LABA and rescue medications. Patients in the DS group will receive a new FS eMDPI device and a new Albuterol eMDPI device at Visit 1 and 1 FS eMDPI device and 1 Albuterol eMDPI device at Visit 2. Periodically after Visits 1 and 2, patients will be shipped a new FS eMDPI device, which they will need to pair with the App. The patient will immediately stop using the old device and switch to the new device. Extra Albuterol eMDPI devices may be shipped as needed, based on the clinical judgment of the investigator. Upon receipt, the patient will pair the new device with the App and will immediately stop using the old device and switch to the new device. To trigger direct-to-patient (DTP) shipments, after Visit 1, the investigational center will receive periodic email reminders to access the interactive response technology (IRT) system to confirm the dose of test investigational medicinal product (IMP) to be shipped to the patient. Confirmation of the dose is required before the next shipment can be sent.

Investigational centers will receive similar instruction regarding features of the App, as well as features of the associated dashboard, which mirrors the digital information obtained from the eMDPIs and App, including frequency and times of SABA rescue use and associated inspiratory flow parameters measured by the eMDPI with each inhalation.

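### The plan contradicts itself on rescue-inhaler supply and return at Visit 2, and the SAP scores weeks with no Albuterol eMDPI in hand as fully SABA-free

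*Protocol*

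**What the plan says.** **Supply.** Protocol 5.1 gives the DS group "a new FS eMDPI device and 1 Albuterol eMDPI device at Visit 1 and 1 FS eMDPI device at Visit 2". The synopsis and Protocol 3.1 instead say "a new FS eMDPI device at Visit 1 and 1 FS eMDPI device and 1 Albuterol eMDPI device at Visit 2". Table 5, under "Dispense test IMP to DS group", marks Albuterol eMDPI at Visits 1 and 2, and its footnote g says "Patients will receive an Albuterol eMDPI device, along with training on use and proper technique, at Visit 1 [Day 1] and Visit 2". SAP 2.1 agrees with Table 5: "a new Albuterol eMDPI device at Visit 1 and 1 FS eMDPI device and 1 Albuterol eMDPI device at Visit 2". Appendix B resupplies at Visit 2 only if needed. So does Figure 2, which adds "Albuterol eMDPI: May be shipped if Visit 2 is not an in-person visit".

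**Return.** Protocol 5.1 and 5.2.3 tell patients to bring back every inhaler at Visit 2; 5.2.3 names partly used ones. Neither excepts the rescue inhaler in use. Protocol 3.1 says that an in-person Visit 2 "will include dispensing of new inhalers to the DS group patients and return of used or unused inhalers".

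**Other relievers.** Protocol 5.6 bars other SABA products in the DS group, apart from nebulized albuterol in the emergency department. Protocol 4.3 makes taking them a reason for withdrawal.

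**Scoring.** Under SAP 6.3.2.1, secondary endpoint #2 is the change from week 1 in weekly SABA use and SABA-free days. A week with no inhalations counts as zero use and 7 SABA-free days. There is no condition that the patient held an inhaler, and SAP 4.3 has no missing-data rule for SABA weeks.

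**The concern.** None, one and conditional cannot all be the Visit 2 rule for the only reliever that DS patients may use outside the emergency department. These patients enter with an ACT score below 19, and about 45 centers need a single instruction. A center that follows 5.1 and applies the return rule at an in-person visit could collect the working rescue inhaler with no scheduled replacement.

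The scoring rule is a separate problem that the same gap would trigger. A week with no inhaler in hand cannot produce recorded inhalations, so it receives the best possible score. Because the endpoint is a change from week 1, the error runs in one direction, toward improvement.

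**Working it through.** **1. Albuterol eMDPI supply, current text only**

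| Place | Visit 1 | Visit 2 |
|---|---|---|
| Protocol 5.1 | one | none |
| Synopsis, Protocol 3.1 | not listed | one |
| Table 5 grid and footnote g | one | one |
| SAP 2.1 | one | one |
| Appendix B | dispensed | if needed |
| Figure 2 | not itemised by visit | if needed; may be shipped if remote |

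The omission at Visit 1 in the synopsis and 3.1 is a drafting gap: the same paragraphs switch patients to Albuterol eMDPI at that visit. The conflict at Visit 2 is substantive.

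**2. How long could a gap last?**

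The documents give no frequency, so these are scenarios for an in-person Visit 2.

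- Table 5 followed, or the inhaler exchanged at the visit: 0 weeks.
- 5.1 followed, replacement sent off schedule (Table 5 footnote h) or dispensed at an on-site Clinically Driven Assessment (Appendix B): possibly days.
- 5.1 followed, albuterol added only to the Week 15 shipment: 3 weeks, 3/24 = 12.5% of treatment. This is an upper scenario.
- No albuterol added at any dose confirmation (Weeks 12, 15, 18 and 21): 12 weeks, 12/24 = 50%. This is a theoretical bound only.

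**3. Effect on secondary endpoint #2 per affected week**

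Assume that need is unchanged from week 1 and that the week is scored under SAP 6.3.2.1.

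- Excess SABA-free days = 7 − week-1 value. For week-1 values of 6, 4 and 2: +1, +3 and +5 days.
- Change in weekly average use = −(week-1 inhalations × 90/7). For 7, 14 and 28 inhalations: −90, −180 and −360 micrograms.

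**4. Effect on the DS group mean**

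Assume that 2% to 10% of patients are affected; the documents give no figure.

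- In one affected week: 0.02 × 1 = 0.02 to 0.10 × 5 = 0.5 days.
- Averaged over the 23 weeks after week 1, with a 3-week gap: 0.02 × 1 × 3/23 = 0.0026 to 0.10 × 5 × 3/23 = 0.065 days per week.

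**5. Run-out of a single inhaler**

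Protocol 5.1.1 gives 200 actuations per albuterol inhaler. One inhaler covers 168 days up to 200/168 = 1.19 inhalations a day. At 2 a day it is empty at day 100, leaving 68 days (9.7 weeks); at 4 a day, at day 50. These figures assume no resupply and only show that run-out is possible.

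**The case against.** **The gap is guarded against.** An in-person Visit 2 pairs return with new inhalers. Appendix B collects only in person and lists resupply beside collection. Sites are asked about albuterol at each dose confirmation, off-schedule replacement shipments are allowed, and on-site Clinically Driven Assessments can dispense. This stands and makes a long gap unlikely. A reader might infer that patients will go 3 to 12 weeks without a reliever; the documents do not support that. What remains is that 5.1 schedules no replacement, and the routes that would supply one under 5.1 rely on site judgment or do not name albuterol.

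**The SAP prevails over the protocol where they differ.** That settles analysis questions. Sites dispense from the protocol, which disagrees with itself.

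**The endpoint measures use, not need.** A day without rescue medication meets the definition whatever the reason, and zero for no inhalations is a natural convention for as-needed medication. This is fair while the patient holds an inhaler. Without one, the inhaler record cannot show use: nebulized albuterol in the emergency department is permitted and would not appear in it.

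**Run-out is speculative.** A reader might infer that an empty inhaler produces false SABA-free weeks. The documents do not establish this. Extra inhalers can be shipped, the device has a dose counter, and the dashboard is checked weekly. Appendix F foresees continued use at zero, and SAP 6.3.2.2 summarises inhalation attempts, so such weeks may not be empty in the data. Setting them to missing would also selectively remove heavier users. This objection stands and shapes the fix.

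**Conclusion.** The supply contradiction and the missing return exception are certain from current text. They warrant correction because they concern the only reliever permitted outside the emergency department; a prolonged gap is unlikely.

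The unconditional zero-use rule is also certain. Its bias runs toward improvement, but its size is unknown and probably small: about +0.003 to +0.07 SABA-free days per week over weeks 2 to 24, if 2% to 10% of DS patients had a 3-week gap and week-1 values lay between 6 and 2 SABA-free days. All of these inputs are assumed.

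A reader might infer that the main result is at risk. It is not: the rule enters only a descriptive, DS-only secondary endpoint, and the primary endpoint, sample size and power do not use it.

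**What to change.** **Protocol and SAP 2.1.** State one rule in the synopsis, 3.1, Figure 2, 5.1, Table 5 and footnote g, Appendix B and SAP 2.1:

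- One Albuterol eMDPI is dispensed at Visit 1.
- At an in-person Visit 2, the albuterol inhaler in use is collected only when a replacement is dispensed at that visit.
- At a remote Visit 2, the patient keeps the current inhaler and a replacement is shipped if needed.

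Add the same exception to the return rule in 5.1 and 5.2.3.

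**SAP 6.3.2.1.** Apply the zero-use, 7-day rule only to weeks in which dispensing, shipment and return records show that the patient held an Albuterol eMDPI. Set other weeks to missing and report how many there are. For possible run-out (200 recorded actuations and no replacement dispensed or shipped), flag and count the weeks and show the summary with and without them, rather than setting them to missing by default.

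**Cost.** A protocol clarification or amendment, a few SAP sentences, some derivation from accountability records and a few missing weekly values. The documents do not describe recording when a shipped inhaler reaches the patient, so possession dates after a shipment will be approximate.
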